4.3.2 Secondary Efficacy Analyses

The percent change from baseline in PVR will be analyzed using the method described for change from baseline in PVR.

In addition, the PVR data (absolute value instead of change from baseline) will be natural log-transformed (\ln) prior to analysis. The dependent variable of the model is the change from baseline for the log-transformed endpoint value (i.e., $\ln(\text{Week 22 value}) - \ln(\text{baseline value})$) or equivalently the log-transformed ratio change from baseline (i.e., $\ln\left(\frac{\text{Week 22 value}}{\text{baseline value}}\right)$). Resultant LS mean estimates will be exponentiated to yield the geometric mean estimates of ratio changes from baseline; resultant LS mean difference estimates from placebo will be exponentiated to derive the geometric mean ratio estimates of ratio changes from baseline that is relative to placebo.

For the proportion of patients who progress to clinical worsening, number (%) of patients progressed in each treatment group and 95% CI will be reported; difference in proportion with 95% CI between treatment groups will be estimated using the method of Miettinen and Nurminen. The effect of APD811 will be compared to placebo using a logistic regression model with model with terms for treatment and baseline WHO/NYHA functional class (II vs. III or IV), and odds ratio and 95% CI will be reported.

4.3.3 Exploratory Efficacy Analyses

Other continuous efficacy endpoints will be analyzed using the above ANCOVA method described for PVR, substituting the relevant baseline measurement as the covariate. Missing values will be imputed with last observation carried forward at Week 22.

Change from baseline in BNP and NT-proBNP after 22 weeks of treatment will be summarized analysed using ANCOVA in the same way as for PVR (using the respective baseline as a covariate instead of baseline PVR). In the event that the normality assumption is violated the analysis will be repeated after the data has been log-transformed.

Categorical change from baseline in WHO/NYHA functional class after 22 weeks of treatment is an ordinal categorical endpoint with 3 categories (Improved, No Change, Deteriorated). It will be analyzed using Cochran-Mantel-Haenszel (CMH) method adjusted baseline WHO/NYHA functional class stratum, and using modified ridit scores to compute the test statistic and p-value for the between-treatment comparison.

For longitudinal change from baseline in 6MWD and WHO/NYHA functional class, a mixed-effects model repeated measures (MMRM) analysis with baseline WHO/NYHA functional class stratum, treatment, week and treatment-by-week interaction as factors and baseline value as covariate will be used to assess the effect of APD811. An unstructured covariance will be used for the within-patient correlation. Appropriate transformations in 6MWD will be applied if necessary (i.e., log transformation). An analysis of categorical WHO/NYHA functional class over time using generalized estimating equations (GEE) proportional odds model will be performed to assess treatment effect on function class shift during entire study period. The GEE model will include appropriate covariates, such as baseline function class and baseline PVR.

For the repeated measures analysis in the MITT population, no explicit imputations will be made. Missing data are assumed to be missing at random (that is, ignorable missingness), which means that the missingness of the data does not depend on the value that is missing after adjusting for the effect of the data that are observed.

For the time to first event of clinical worsening endpoint, the duration is defined as from randomization to first occurrence of clinical worsening, otherwise it will be censored at the last recorded date of clinical worsening event assessment or end of study, whichever is later. The cumulative event rates and graphic presentation will be estimated and produced using the Kaplan-Meier method. Non-parametric methods such as the log-rank test stratified by baseline WHO/NYHA functional class stratum will be utilized to compare the survival curve by treatment group. A Cox proportional hazards model will be applied to compare the hazard rates between treatment groups. The model will include treatment, baseline PVR and WHO/NYHA stratum as factors. The hazard ratio (HR) between the treatment groups (APD811 /placebo) will be estimated. The 95% CIs around the estimated HR along with event rates per 100 person years will be presented. Analytical and graphical methods will be employed to verify the proportional hazard assumption. The proportional hazards assumption will be tested by including the factor $\text{treatment} * \log(\text{time})$ in the model; nonsignificance ($p > 0.05$) of this factor implies proportionality, i.e., constancy of treatment effect over time.

Other exploratory analyses may be performed to further assess treatment effects on efficacy measures, and relationships between during treatment measures. There will be no inferential testing for these analyses and only point estimate and corresponding confidence interval will be reported. Analyses related to baseline subgroup will be described in section 6.2. Followings are potential exploratory analyses.

- Relationships between study drug exposure (intensity and duration) and efficacy measures (PVR, 6MWD, WHO/NYHA FC, BNP/NT-proBNP, etc.)
- Correlations between Week 22 efficacy measures (PVR vs. 6MWD, PVR vs. WHO/NYHA FC, 6MWD vs. WHO/NYHA FC, BNP/NT-proBNP vs. PVR, BNP/NT-proBNP vs. 6MWD, etc.)
- Proportion of patients achieving $\geq 10\%$ 6MWD increase from baseline at Week 22
- Proportion of patients achieving ≥ 440 meters 6MWD at Week 22
- Proportion of patients achieving clinical improvement at Week 22, such as $\geq 10\%$ 6MWD increase from baseline and WHO/NYHA FC I or II
- Proportion of patients achieving normalized PVR (< 240 units) at Week 22
- Proportion of patients achieving $\geq 15\%$ in PVR reduction from baseline at Week 22
- Analysis of REVEAL score shift at end of study in comparison with baseline

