## 1.1 Background Information

## 1.1.1 Rationale for Proposed Clinical Study

Despite recent advancements in treatment options, PAH remains a fatal disease with approximately 15% mortality within 1 year and a 3-year survival rate between 35-75% depending on PAH etiology and co-morbid conditions. There is a significant need for alternative treatments for this disease. APD811, an oral non-prostanoid IP receptor agonist, could be an effective and convenient treatment option.

APD811 has been characterized in both single and multiple dose studies in a healthy volunteer population. The safety profile suggests that dose-related pharmacology at the IP receptor is occurring within the dose range of 0.01-0.2 mg with adverse effects consistent with those reported for IP agonists. The pathophysiology of PAH may be associated with changes in prostacyclin receptors within the pulmonary vascular circulation, and lead to differing responses than in healthy volunteers. This study is being undertaken to define the appropriate dose titration regimen and assess the hemodynamic effects of APD811 in PAH patients.

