# 9.5.2.3 Exploratory Efficacy Analysis

- Change from baseline in BNP and NT-proBNP after 22 weeks of treatment
- Change from baseline in SVR after 22 weeks of treatment
- Change from baseline in WHO/NYHA functional class after 22 weeks of treatment

Other continuous efficacy endpoints will be analyzed using the above ANCOVA method described for PVR, substituting the relevant baseline measurement as the covariate. Missing values will be imputed with last observation carried forward.

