4 EFFICACY ANALYSES

4.1 Efficacy Endpoints

A table is provided in Appendix 3 summarizing the efficacy variables and their analysis populations.

Primary Endpoints

The primary endpoints are listed below:

- Change from baseline in PVR after 22 weeks of treatment
- Change from baseline in 6 MWD after 22 weeks of treatment.

Secondary Endpoints

Secondary efficacy variables include:

- Percent change from baseline in PVR after 22 weeks of treatment
- Proportion of patients who progress to clinical worsening

Exploratory Endpoints

The exploratory efficacy endpoints are listed below:

- Change from baseline in BNP and NT-proBNP after 22 weeks of treatment
- Change from baseline in SVR and other hemodynamic parameters (listed in Section 1.2.2.3) after 22 weeks of treatment
- Change from baseline in WHO/NYHA functional class in numeric scale after 22 weeks of treatment
- Proportion of patients in categorical change of WHO/NYHA function class after 22 weeks of treatment. Three ordinal categories are defined as Improved, No Change, and Deteriorated, in comparison with baseline
- Longitudinal change from baseline in 6 MWD up to 22 weeks
- Longitudinal change from baseline in WHO/NYHA functional class in numeric scale up to 22 weeks
- Time to first event of clinical worsening, the duration is defined as from randomization to first occurrence of clinical worsening, otherwise it will be censored at the last record date of clinical worsening event assessment or end of study, whichever is latest.

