4.3 Approaches to Efficacy Analysis

4.3.1 Primary Efficacy Analysis

The primary efficacy hypothesis regarding the superiority of APD811 to placebo will be assessed in a stepwise manner. First, the statistical significance of APD811 versus placebo result will be determined for the change from baseline in PVR at the end of 22 weeks of treatment. If the result is significant ($p < 0.05$, two-sided), the primary hypothesis will be considered satisfied and this study will be declared positive. Subsequently, the change from baseline in 6MWD will only be formally tested if the change from baseline in PVR is significant. This testing procedure preserves the overall Type I error rate for testing the primary efficacy hypothesis.

In this first-in-patient Phase 2 study in PAH patients, there is a clinical rationale to specify two important primary endpoints: the key hemodynamic parameter, PVR; exercise capacity as measured by 6MWD. Right heart catheterization from which PVR is derived only takes place at Screening and Week 22; 6MWD is measured at Screening, baseline, and at 5 post-baseline specified time points.

In cases of missing data occurring at Week 22, the following missing data handling rules will apply.

For PVR, assessments measured at Week 22 or at time of early withdrawal will be included in the analysis. Missing data at Week 22 will be imputed using the method of multiple imputation as outlined in Section 7.4 and detailed in Appendix 4. For 6MWD, missing values will be imputed with the last observation carried forward (LOCF), except if any patient withdraws early due to death or due to clinical worsening without a 6MWT being measured at a termination visit, a worst value of 0 for 6MWD will be imputed. Baseline assessments will not be carried forward.

To further assess missing data impacts on primary analyses, the completers analyses without data imputation will be performed and compared with additional sensitivity analyses specified in Section 7.4.

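### SAP 4.3.3 carries WHO/NYHA class forward to Week 22 with no rule for death, so a patient who dies can be scored as unchanged or improved

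*SAP*

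**What the plan says.** SAP 4.1 lists two Week 22 functional class endpoints among the exploratory endpoints. One is numeric: "Change from baseline in WHO/NYHA functional class in numeric scale after 22 weeks of treatment". The other is ordinal: "Three ordinal categories are defined as Improved, No Change, and Deteriorated, in comparison with baseline". Neither gives death a place on its scale.

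The analysis is in SAP 4.3.3, which opens: "Other continuous efficacy endpoints will be analyzed using the above ANCOVA method described for PVR, substituting the relevant baseline measurement as the covariate". The next sentence is the missing-data rule: "Missing values will be imputed with last observation carried forward at Week 22". Protocol 9.5.2.3 has the same rule beneath a list that names functional class: "Missing values will be imputed with last observation carried forward". The ordinal endpoint comes two paragraphs later in SAP 4.3.3: "It will be analyzed using Cochran-Mantel-Haenszel (CMH) method adjusted baseline WHO/NYHA functional class stratum", with modified ridit scores and no missing-data rule of its own. For the repeated-measures analyses the SAP makes no imputation and assumes data missing at random.

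For 6MWD, SAP 4.3.1 also uses LOCF, but departs from it when a patient withdraws early because of death, or because of clinical worsening with no walk test at a termination visit. Then "a worst value of 0 for 6MWD will be imputed". Protocol 9.5.2.1 contains the same exception.

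SAP Appendix 3 assigns both Week 22 class endpoints to the MITT and completers populations.

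**The concern.** The 6MWD exception shows that the sponsor saw the problem: carrying a last value past death records the worst outcome as whatever the patient last managed. The exception was not extended to functional class, which has the same problem.

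Change in functional class is a stated exploratory objective. Under SAP 4.3.1 and 6.3 it is formally tested at two-sided 0.05 once PVR is significant. An omitted death rule helps whichever arm has more deaths without a recorded decline. SAP 4.3.3 also lists a Week 22 correlation between 6MWD and functional class, which would pair 0 m with a carried-forward class for the same deceased patient.

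Nothing else in the plan corrects this. The introduction to the sensitivity analyses in SAP 7.4 mentions selected exploratory endpoints, but the analyses listed are completers analyses of primary and secondary endpoints, worst-case imputation for PVR, and a discontinuation-as-event analysis for clinical worsening. None scores death as worst for functional class. The completers analysis of class drops deaths, and the repeated-measures models have no death rule.

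**Working it through.** The plan states no figure that depends on this rule, so there is none to reproduce. The check applies the written rules to patient records and then sizes the effect.

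**1. The rules applied to two hypothetical records, neither with a termination visit**

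| Record | Numeric class change (SAP 4.3.3) | Category, if LOCF applies | 6MWD (SAP 4.3.1) |
|---|---|---|---|
| Class III at baseline, III at Week 14 (Day 98), dies Day 110 | 3 − 3 = 0 | No Change | 0 m |
| Class III at baseline, II at Week 10 (Day 70), dies Day 90 | 2 − 3 = −1 | Improved | 0 m |

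The numeric column follows directly, because numeric change at Week 22 has no other stated method. A value to carry forward will usually exist, since class is assessed at every visit (Protocol 6.7). A patient who dies before any post-baseline class is outside MITT and drops out altogether.

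**2. The ordinal endpoint under each reading**

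If LOCF applies, the category column above holds. If it does not, no rule covers the missing value and the patient is dropped or handled ad hoc. Neither reading counts the death as Deteriorated.

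**3. How many patients**

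The documents give no expected mortality for this trial, so a range is needed. All rows assume constant hazard over 22 weeks, with 40 APD811 and 20 placebo patients (Protocol 9.3).

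| Source | 22-week risk | Deaths in 60 |
|---|---|---|
| Protocol 1.1.1: "PAH remains a fatal disease with approximately 15% mortality within 1 year" | 1 − 0.85^(22/52) = 6.6% | 4.0 (2.7 APD811, 1.3 placebo) |
| Protocol 1: median survival of about 7 years (364 weeks) in a more recent cohort | 1 − 0.5^(22/364) = 4.1% | 2.5 (1.6 and 0.8) |
| Assumed lower value for a stable, treated population | 2% | 1.2 (0.8 and 0.4) |

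These are upper counts, because only deaths with no recorded decline are mis-scored.

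**4. Weight of one patient**

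One death moves the percentage Deteriorated by 1/40 = 2.5 points in the APD811 arm, or 1/20 = 5 points in the placebo arm.

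**5. Effect on the comparison**

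At equal hazard both arms lose the same expected share (6.6 points at most), so the expected difference does not change. With unequal splits, scoring deaths as Deteriorated shifts the difference (APD811 minus placebo) by:

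- 3 v 1 deaths: 3/40 − 1/20 = +2.5 points
- 4 v 0 deaths: 4/40 − 0/20 = +10 points
- 0 v 3 deaths: 0/40 − 3/20 = −15 points

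As an illustration on assumed counts (Improved / No Change / Deteriorated), take 12/26/2 on APD811 and 3/14/3 on placebo, with deaths held in No Change. A single-stratum CMH test with modified ridit scores gives p = 0.108. Moving the deaths to Deteriorated gives p = 0.188 (3 v 1), 0.361 (4 v 0) or 0.021 (0 v 3). The last two splits are deliberately extreme.

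**6. Why assigning class IV is not enough**

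Setting a death to class IV gives a numeric change of +2 from baseline class II and +1 from class III, but 0 from class IV. A baseline class IV patient who dies would still score no change.

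**The case against.** The strongest objection concerns scope. The LOCF sentence closes a paragraph about continuous endpoints, and the ordinal endpoint is treated separately with its own method. A reader might infer that the SAP expressly scores deaths as No Change in the CMH analysis. It does not say so. For that endpoint the defect is an unstated rule, though neither way of filling the gap counts death as deterioration.

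A reader might also infer that withdrawals for clinical worsening add substantially to the problem. Mostly they should not. The combined criterion in Protocol 6.9 itself requires a worse class than baseline, which LOCF carries forward correctly if it is the last value. Patients who meet any criterion should undergo early-termination procedures, and the end-of-study assessments include functional class (Protocol 6.9, 6.15.1 and 7.4.3.1). What remains is chiefly death without a prior recorded decline, plus an occasional withdrawal triggered by a medication change with the termination assessment missed. The documents give no basis for a count of the latter.

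On size, 15% a year describes PAH generally. This trial requires stable therapy for 3 months and excludes recent acute decompensation, low systolic pressure and recent inotropes, so mortality may well be lower. That stands.

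Finally, an exploratory endpoint may have a different missing-data rule from a primary one without contradiction, and the SAP's LOCF agrees with the protocol. Deaths also remain visible in the clinical worsening endpoints and in 6MWD. These points limit the importance of the gap. They do not make a score of no change or improvement right for a patient who has died.

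**Conclusion.** The point holds for the numeric endpoint as written: a patient who dies with an unchanged or improved last class scores 0 or better on functional class and 0 m on 6MWD. For the three-category endpoint the handling is unstated, and death is not counted as deterioration on either reading.

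The size is probably 1 to 4 patients of 60, resting on assumed 22-week mortality of 2% to 6.6% at constant hazard, with 4.1% from the 7-year median survival. A reader might take 6.6 points as the bias in the treatment comparison. It is an upper figure within each arm, and it cancels in expectation when the arms have equal hazard. The comparison is biased only if such deaths split unequally, and the p-values above rest on assumed class counts.

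The PVR and 6MWD conclusions are unaffected. This is a modest defect in an exploratory endpoint, worth correcting because the plan already contains the model for the correction.

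**What to change.** Add to SAP 4.3.3 a rule parallel to the one for 6MWD. A patient who dies before the Week 22 assessment, or who withdraws for clinical worsening with no termination-visit class assessment, is:

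- kept in the analysis set;
- classed Deteriorated in the CMH analysis;
- given the worst rank for numeric change, in a rank-based analysis. The stratified Wilcoxon test already named in SAP 4.3.1 would serve. A worst rank avoids the baseline class IV problem and does not require a value beyond the scale.

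The same text should say that LOCF applies to the three-category endpoint for other missing values, if that is intended.

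The cost is a sentence or two in the SAP and a few lines of programming, with no new data. The downside is a few assigned values in an exploratory endpoint, including the occasional worsening withdrawal whose last recorded class had not declined. The change should be in place before unblinding.

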## 5.6.2 Study Transition Period

At the end of the treatment period and after all Week 22 study assessments are performed, patients who are eligible and who elect to enroll in the APD811-007 study, will continue current treatment through the 3 week (±1 week) follow-up visit (Week 25). During this 3-week (±1 week) period, the individual patient database will be locked allowing for

subsequent unblinding of the individual patient and enrollment into the APD811-007 OLE. The Week 25 visit will serve as the baseline visit for the APD811-007 OLE study.

For patients who do not enter the extension study, study drug is stopped after the treatment period at the Week 22, End of Study Visit.

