	
To be eligible to enroll in the extension study APD811-007, patients must complete study APD811-003. Additionally, placebo treated patients who discontinue study drug treatment due to clinical worsening in APD811-003 will be permitted to enroll in APD811-007, upon approval of the medical monitor, provided that all end of study procedures including right heart catheterization are performed per protocol.
 
Patients will be receiving concomitant oral disease-specific PAH therapy consisting of an endothelin receptor antagonist (ERA) and/or an agent acting on the nitric oxide pathway, a PDE5 inhibitor or a soluble guanylate cyclase stimulator, provided the dose has remained stable for at least 3 months prior to the start of Screening. Patients should continue the same dose and regimen of these medications for the duration of the study.
 
The use of the following therapies, which may affect PAH, are permitted:
 
Vasodilators (including calcium channel blockers), digoxin, spironolactone, or L-Arginine supplementation; if on a stable dose for at least 1 month prior to the start of Screening and should remain unchanged during the study.
 
Doses of spironolactone and digoxin may be held or reduced as necessary to protect the patient’s safety. Doses may not be increased in the month before Day 1 and during the controlled study.
 
Diuretics may be dosed as clinically indicated throughout the study.
 
Intravenous inotropes within 1 month of starting Screening are not permitted.
 
In an attempt to maintain balance across treatment groups, the following stratification factor will be utilized during patient randomization:
 
 • Baseline WHO/NYHA Functional Class (Class II vs III or IV) 
If a patient’s participation in the study is discontinued early, all end of study (EOS) safety and efficacy evaluations are to be performed as part of the Week 22/Early Termination visit. The EOS visit for early terminations will be followed by a follow-up visit to ensure appropriate patient safety at Week 25. If the patient is unable to return for the follow-up visit, AE and concomitant medication follow-up may be conducted by telephone.

Study Site:
	
Multiple centers in United States, Europe, and Australia.

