7.4 Handling of Missing Data and Sensitivity Analysis

For the ITT analysis of PVR missing week 22 assessments will be derived using the method of multiple imputation via the SAS/STAT procedure PROC MI and the fully conditional

specification (FCS) method to create 100 imputations resulting in 100 complete datasets. The 100 imputed datasets will then be analyzed using the methods described in Section 4.3.1, with the results of the analyses performed on the 100 datasets combined via PROC MIANALYZE. The imputation model will include the following variables: treatment, baseline PVR, baseline NYHA/WHO functional class category, baseline PAH therapy, baseline values for 6MWD, BNP, NT-proBNP, etiology, last on-treatment 6MWD and whether or not a patient experienced clinical worsening. It is anticipated that the imputation model will converge but should it not do so terms will be removed from the model to achieve convergence. The effects of any such model adjustment will be investigated.

To assess the impact of missing data and robustness of the results, the following sensitivity analyses will be performed for the primary, secondary and selected exploratory endpoints:

- Completers population analyses on primary and secondary efficacy endpoints will be performed without missing data imputation.
- Worst case imputation. For PVR, in all-treated patients, prior to ANCOVA analyses as detailed in Section 4.3.1 missing data at Week 22 due to any reason will be imputed by taking:
 - the worst percentage change from baseline in all patients regardless of treatment group.
 - the baseline observation carried forward.
- An additional 'tipping point analysis' *may* be performed for PVR, post-hoc, in the event that the primary analysis is statistically significant and at least 1 of the worst case imputation analyses yields a non-significant result.

For the proportion of patients who progress to clinical worsening, a sensitivity analysis to assess the impact of missing data will be performed wherein all patients who prematurely discontinue treatment for any reason will be considered to have had a clinical worsening event.

- Imputation of missing or incomplete AE start date
 - If year part of AE start date is missing, then the year of the first treatment date will be assigned.
 - If both month and day part of AE start date are missing, and the year part is the same as year of the first treatment date, then the first treatment date will be assigned;

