8.3 Description of Data Handling Procedures Prior to Unblinding

All data will be screened, reviewed, and declared clean before data are unblinded according to Novella (Data Management CRO) guidelines and standard operating procedures. At the end of the treatment period and after all Week 22 study assessments are performed, patients who are eligible and who elect to enroll in the APD811-007 study, will continue current treatment through the 3 week (± 1 week) follow-up visit (Week 25). During this 3 week (± 1 week) period, the individual patient database will be locked allowing for subsequent unblinding of the individual patient and enrollment into the APD811-007 OLE Study. For patients who do not enter the extension study, study drug will be stopped after the treatment period at the Week 22, End of Study Visit and their individual patient database will not be locked, frozen or unblinded until the end of the study.

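### Time to first clinical worsening: the censoring date can fall after the last worsening assessment, because end of study is not defined for this exploratory endpoint

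*SAP*

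**What the plan says.** SAP 4.1 lists time to first clinical worsening as an exploratory endpoint. For patients without an event it states: "otherwise it will be censored at the last record date of clinical worsening event assessment or end of study, whichever is latest". SAP 4.3.3 repeats the rule: "otherwise it will be censored at the last recorded date of clinical worsening event assessment or end of study, whichever is later". From these times the SAP plans Kaplan-Meier curves, a stratified log-rank test, a Cox hazard ratio and event rates per 100 person-years.

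Neither section says which date end of study is. Two usages appear elsewhere:

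- **Patient level.** The SAP Synopsis (Study Design) has "end of study (EOS) safety and efficacy evaluations are to be performed as part of the Week 22/Early Termination visit".
- **Trial level.** SAP 8.3, on patients who do not enter the extension, has "their individual patient database will not be locked, frozen or unblinded until the end of the study".

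The Protocol and SAP synopses also schedule a Week 25 follow-up for early terminators. It may be done by telephone, and then covers adverse events and concomitant medication.

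The related secondary endpoint is "Proportion of patients who progress to clinical worsening" (SAP 4.1). SAP 4.3.2 analyses it as a crude percentage, "number (%) of patients progressed in each treatment group and 95% CI will be reported", with a Miettinen-Nurminen difference and a logistic regression. It gives no rule for a patient who leaves without a recorded event. SAP 7.4 adds a sensitivity analysis of the proportion in which "all patients who prematurely discontinue treatment for any reason will be considered to have had a clinical worsening event". No sensitivity analysis is given for the time-to-event endpoint.

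**The concern.** Taking the later of two dates changes a patient's censoring date only when end of study falls after the last worsening assessment. The interval added is then, by construction, time in which nobody assessed the patient for worsening. When the two dates coincide, or the assessment is the later one, the end-of-study limb does nothing. So the limb contributes no valid follow-up and can contribute invalid follow-up.

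If it does, early dropouts stay in the risk set as event-free after they have left. Kaplan-Meier risk and person-year rates are then too low in any arm with dropout, and the comparison shifts in favour of the arm with more dropout. That could be the active arm in a trial that titrates each patient to tolerability, although the documents do not say so.

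**Working it through.** **1. The plan's own figures.** The documents give no event rate, event count or power for clinical worsening. The relevant planning figure is dropout of up to 30% before the repeat catheterization (Protocol 9.3, SAP 7.1). It reproduces: 28/0.7 = 40 and 14/0.7 = 20, and 28 against 14 gives 90.3% power for PVR (noncentral t), as stated. No split of dropout by arm is given.

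**2. What each reading of end of study does to a Week 6 dropout**

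- Own early-termination visit, worsening assessed there: no time added.
- Nominal Week 22: 22 − 6 = 16 weeks added.
- Week 25 telephone contact: up to 25 − 6 = 19 weeks added. Such a call could reveal a death or a new PAH drug, but not the combined walk-distance, functional-class and right-heart-failure criterion.
- Trial-level date: at least to the end of the patient's scheduled follow-up, and possibly longer.

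**3. Unequal dropout, no drug effect.** Assumptions, not document figures: 22-week risk 15% in both arms; dropout d = 0.30 on APD811 and 0.10 or 0.15 on placebo; all dropout at week w = 5 or 8.

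Observed person-time per patient, ignoring the small loss after events, is 22(1 − d) + wd. With time credited to Week 22 it is 22 in both arms. Expected events are proportional to observed person-time, so the apparent rate ratio is the ratio of the observed person-times. The crude proportion is 0.15(1 − d) + d(1 − exp(−λw)), with λ = −ln(0.85)/22 = 0.00739 per week.

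| w | d placebo | Weeks, APD811 | Weeks, placebo | Rate ratio | Crude %, APD811 vs placebo | Odds ratio |
|---|---|---|---|---|---|---|
| 5 | 0.10 | 16.9 | 20.3 | 0.83 | 11.6 vs 13.9 | 0.81 |
| 5 | 0.15 | 16.9 | 19.45 | 0.87 | 11.6 vs 13.3 | 0.85 |
| 8 | 0.10 | 17.8 | 20.6 | 0.86 | 12.2 vs 14.1 | 0.85 |
| 8 | 0.15 | 17.8 | 19.9 | 0.89 | 12.2 vs 13.6 | 0.88 |

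The true ratio is 1 in every row. Person-time is inflated by 24-30% on APD811 (22/17.8 to 22/16.9) and by 7-13% on placebo (22/20.6 to 22/19.45). With nobody censored before Week 22, the Kaplan-Meier risk at Week 22 equals the crude proportion.

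**4. Equal dropout.** Assume 20% risk and 30% dropout in both arms, with exponential times: λ = −ln(0.8)/22 = 0.01014, μ = −ln(0.7)/22 = 0.01621, s = λ + μ = 0.02636.

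- Events per patient: (λ/s)(1 − exp(−22s)) = 0.169.
- Observed person-time: (1 − exp(−22s))/s = 16.7 weeks.
- Credited person-time: 16.7 + (0.271 × 22 − 2.69) = 20.0 weeks, about 19% more. Here 0.271 is the proportion dropping out event-free, and 2.69 is the contribution of their observed time to the mean.
- Rate per 100 person-years, at 52.18 weeks per year: 52.9 observed against 44.3 credited.
- Kaplan-Meier risk at Week 22: about 20% against about 17%.
- Hazard ratio in a large simulation: 0.98 under both rules, so unaffected.

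If dropout is 30% against 10% instead, the rate ratio becomes 44.3/50.1 = 0.88.

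**The case against.** **The natural reading may be harmless.** End of study is an established patient-level visit in both documents, and worsening is assessed there. A trial-level date would also make the comparison of two dates redundant, since no assessment could be later. This stands as a reason to think the sponsor meant the patient's own visit. It does not settle the text, because the endpoint leaves the term undefined and SAP 8.3 uses nearly the same words for the whole trial.

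**Dropouts are not all non-events.** A reader might infer that every dropout counts as event-free in the secondary proportion. The documents do not support that. Death and clinical worsening are events, and both are listed reasons for discontinuing. Patients with no post-randomization measurement fall outside the MITT population. SAP 7.4 already counts all premature discontinuations as events, and Appendix 3 adds a completers analysis. What remains is that event-free MITT dropouts are non-events by default in the main analysis. The SAP 7.4 analysis is an opposite extreme: with 20% risk in both arms and dropout of 40% against 10%, it gives 52% against 28%, where the crude figures are 15.8% and 19.0%.

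**The comparative bias needs unequal dropout.** This stands in full. It is also small beside the sampling error. At 15% risk about 6 and 3 events are expected (40 × 0.15, 20 × 0.15), the standard error of a log ratio is about √(1/6 + 1/3) = 0.71, and the 95% interval spans a factor of about exp(1.96 × 0.71) = 4 each way.

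**Larger remedies go too far.** One might want to stop all follow-up at Week 22, because patients not entering the extension are off drug afterwards: "study drug is stopped after the treatment period at the Week 22, End of Study Visit" (Protocol 5.6.2). A hard cutoff would discard fatal events within 14 days of stopping treatment, which the endpoint definition counts. Moving the secondary comparison to a log-rank test would depart from the logistic regression in Protocol 9.5.2.2 and is a trade-off, not a correction.

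**Conclusion.** The point holds as an ambiguity in a stated rule. Under three of the four readings considered, early dropouts are credited with time in which worsening was not assessed. Kaplan-Meier risk and person-year rates are then understated even with equal dropout (20% to about 17%, and 52.9 to 44.3 per 100 person-years, in the illustration). With assumed dropout of 30% against 10-15%, a true rate ratio of 1 becomes 0.83-0.89. If end of study is the patient's own visit with worsening assessed there, the effect is about zero. Event risks, dropout by arm and dropout timing are all assumptions.

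A reader might go further and conclude that the analyses are biased toward APD811. The documents do not establish this: it needs both an unfavourable reading of the term and more dropout on the active arm. Severity is minor, because the censoring rule governs an exploratory endpoint.

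**What to change.** In SAP 4.1 and 4.3.3, replace the rule with censoring at the date of the patient's last clinical-worsening assessment. State that fatal events within the endpoint's 14-day window after stopping treatment still count as events, even if they come after that assessment. This discards no assessed follow-up and changes nothing if the patient-level reading was intended.

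For the secondary proportion, keep the protocol's logistic regression and the SAP 7.4 sensitivity analysis. Report the Week 22 Kaplan-Meier risk by arm beside the crude percentage, so that the effect of counting event-free dropouts as non-events can be seen.

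The cost is SAP wording and one further reported estimate from an already planned Kaplan-Meier analysis. No data collection changes. The downside is that Kaplan-Meier assumes non-informative dropout, which is doubtful if patients leave for intolerance or decline. The SAP 7.4 analysis helps to judge this for the proportion but does not cover the time-to-event analysis.
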